Objective: This study aims to assess the levels of lens spoilage under standard wear and disinfection practices in order to determine the optimal lens replacement frequency of OK lenses. Further, this study will evaluate the health of anterior surface of the eye and lens comfort levels during one-year overnight use of OK lenses.

III. STUDY DESIGN

The proposed study uses a *prospective, observational quasi-experimental research design* where the contact lens spoilage from same participants will be observed over the time before and after contact lens wear. This design is well-suited for monitoring real-world lens wear and eye health outcomes. The term "quasi-experimental" suggests that the non-randomized, single group study, which is appropriate for this type of longitudinal observations studies.

Individuals (between 18 to 40 years of age) with a refractive error between -1.00 and -4.00D of sphere and astigmatism $\leq 2.50D$ will be recruited in the study. The eligible participants will receive study OK lenses during the dispensing visit, following the screening visit. Participants will attend total eight visits, including a follow up visit 2 weeks after the lens cessation which will

allow to assess the recovery or stabilization of eye surface measurements. At each visit, the anterior surface of the eye and comfort levels will be assessed using clinical microscope and by administering questionnaires. Further, lens fit assessment and care regimen compliance will be monitored closely. A photographic method will be used to qualitatively assess lens spoilage at each visit. Furthermore, during the lens dispensing visit, the 6-month visit, and the 1-year visit, lens deposition will be quantitatively evaluated using established standard laboratory procedures. This will allow us to investigate the long-term changes in the eye surface during the OK lens wear and to determine their association with eye discomfort. Additionally, the levels of lens spoilage at different time points and their association with eye discomfort will determine the optimal replacement schedule of OK lens.

Participants will be monitored for:

- Signs of eye surface changes (e.g., corneal staining, conjunctival health).
- Contact lens comfort measured using standardized surveys (e.g., OSDI, CLDEQ-8).
- Lens spoilage (e.g., surface scratches, protein deposition).

Outcomes:

- **Primary outcome:**
 - OK lens spoilage grading scores.
- **Secondary outcomes:**

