4. Quantitative assessment of the lens surface protein deposition: The amount of protein and lipid deposited on the lens surface will be quantified using standardized lab procedures. This assessment will be performed on the right eye lens at the base line visit, 6-month visit and the left eye lens at the 12-month visit. At 6-month visit, a new lens with similar parameters will be dispensed for the right eye, as the original lens will be used for quantitative assessment.

IV. PARTICIPANT SELECTION

Number of participants

We are planning a study with an ordinal data response variable from matched pairs of study participants. We estimate that the difference in the lens spoilage grading between matched pairs is normally distributed with a standard deviation 0.9. To detect a true mean difference of 1.90 between pairs, we will need 12 subjects to achieve 80% power, assuming a Type I error rate of 0.05. To account for a 20% dropout rate, a total of 16 participants will be recruited. We will keep screening until we have met that target.

Inclusion Criteria

- Age between 18 to 40
- Have refractive error between -1.00 and -4.00D of Sphere, Astigmatism \leq 2.50D.
- Good eye health with no history of eye trauma or surgery, no eye disease
- Soft contact lens wearers willing to discontinue lens wear for at least 24 hours before participation. Individuals with or without a history of wearing rigid lenses (including orthokeratology) for a short-term (\leq 3months) and have discontinued wearing them for one month.
- Good general health and no medications which may influence eye health.
- Willing and able to comply with the research procedures and follow-up schedule.

Exclusion Criteria

- Age less than 18 years-old and more than 40 years-old
- Refractive error between less than -1.00D and more than -4.00D, astigmatism $>$ 2.50

Recruitment

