Potential participants will be provided with Participant Information Sheets and Consent form (PISCF) to read, outlining the potential risks and benefits. There will be an opportunity to clarify details regarding the research study before participating. Interested participants, who contacted the investigators will be provided with PISCF through emails. All participants will be above the age of 18 years and will have adequate English language to be able to sign their consent for the study. The informed consent information sheet is attached.

Participants will be given at least 24 hours to review the PISCF before the screening visit. If they have any questions, they can contact the researchers. Written consent will be obtained at the screening visit, where participants will return the signed PISCF to the investigators. Only after consent is provided will the screening visit proceed.

Enrolment Procedure

The participant will only be considered enrolled into the study after the informed consent process has been completed and the participant has met all inclusion criteria and none of the exclusion ones. The participant will receive a study enrolment number, and this will be documented on all study documents.

V. STUDY OUTLINE

Table 3. Study outline and visit details.

Procedures/ Data (Y/N)	Screening visit (60 min)	Baseline visit (45-60 min)	1-day visit (45-60 min)	7-days visit (45-60 min)	21-days visit (45-60 min)	6-months visit (45-60 min)	12-month visit (45-60 min)	2-wk lens cessation visit (45-60 min)
Visit Window	N/A	N/A	N/A	± 2 days	± 2 days	± 7 days	± 7 days	± 2 days
Informed Consent	Y	N	N	N	N	N	N	N
Meet Inclusion / Exclusion Criteria	Y	N	N	N	N	N	N	N
Questionnaires	N	Y	Y	Y	Y	Y	Y	Y
Visual Acuity	Y	Y	Y	Y	Y	Y	Y	Y
Refraction	Y	Y	Y	Y	Y	Y	Y	Y
Anterior Eye Health Check	Y	Y	Y	Y	Y	Y	Y	Y

Procedures/ Data (Y/N)	Screening visit (60 min)	Baseline visit (45-60 min)	1-day visit (45-60 min)	7-days visit (45-60 min)	21-days visit (45-60 min)	6-months visit (45-60 min)	12-month visit (45-60 min)	2-wk lens cessation visit (45-60 min)
Visit Window	N/A	N/A	N/A	± 2 days	± 2 days	± 7 days	± 7 days	± 2 days
Corneal Topography	Y	Y	Y	Y	Y	Y	Y	Y
OK Lens Parameter Selection	N	Y	N	N	N	N	N	N
Lens Fitting Assessment	N/A	Y	Y	Y	Y	Y	Y	N
Lens Spoilage Assessment (qualitative)	N/A	Y	Y	Y	Y	Y	Y	N
Lens Spoilage Assessment (quantitative – protein assay)	N/A	Y	N	N	N	Y	Y	N
Lens compliance using “O-K Wear Time Journal”	N/A	Y	Y	Y	Y	Y	Y	Y

VI. SAFETY

1. Study Procedure Risks:

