The study hypothesises that OK lens spoilage, including scratches and surface deposits, as well as eye discomfort levels, will progressively worsen across the visits at baseline visit, 6 months and 12 months visit. All the statistical methods will be aimed to address the given hypothesis.

Once all data are collected, different tests will be conducted to establish whether they follow normal distributions. This step will ensure us to choose the appropriate statistical test based on the data distribution. Continuous variables will be expressed as means \pm standard deviations, while categorical variable will be reported as medians and interquartile ranges (IQR). The time

effect (baseline, 6month and 12 month) and between-group differences in lens deposition levels, lens wettability scores, eye discomfort data from questionnaires, and eye surface changes will be tested with repeated measures ANOVAs (post-hoc tests) or Friedman test, with Bonferroni correction, where appropriate. This method will assess whether there are significant differences in spoilage across the three time points. If significant, post-hoc tests will help confirm if the worsening follows a progressive pattern from baseline visit to 12 months.

This study will use Spearman's correlation test to evaluate the correlations between the questionnaires scores (eye discomfort levels) and clinical test results (deposition and scratches). This correlation analysis will determine how these subjective and objective measures relate, further supporting the study hypothesis if a correlation is found. A value of $P < 0.05$ will be considered as significant. Furthermore, we determine to explore the association between OK lens replacement schedules and keratitis risk. By tracking lens spoilage, patient symptoms, and clinical indicators of infection over 12 months, we intend to gather preliminary data on infection risk. Given the difficulty of detecting keratitis with a small sample, we will use lens spoilage indicators as proxies for risk. We will also track all eye-related adverse events. While we may not establish a definitive keratitis rate, our approach will generate valuable insights on factors affecting OK lens-related health and guide future research on optimal replacement schedules to reduce keratitis risk.

VIII. STORAGE AND ARCHIVING OF STUDY DOCUMENTS.

Data format and storage location

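### In the protein and lipid assay the 12-month lens is always the left one, so a right-left difference cannot be told apart from change up to 12 months; the source of the baseline lens also needs stating.

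*Protocol*

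**What the plan says.** Protocol section III, Detailed Study procedure, item 4, sets out the quantitative assay of protein and lipid. It is "performed on the right eye lens at the base line visit, 6-month visit and the left eye lens at the 12-month visit". No randomisation or alternation of eyes is mentioned. At 6 months, "a new lens with similar parameters will be dispensed for the right eye, as the original lens will be used for quantitative assessment".

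The Study Design text gives the same three time points: "during the lens dispensing visit, the 6-month visit, and the 1-year visit, lens deposition will be quantitatively evaluated using established standard laboratory procedures". Table 3 (section V) marks the row "Lens Spoilage Assessment (quantitative – protein assay)" as done at the baseline, 6-month and 12-month visits. Baseline is also the visit at which the lenses are handed out: "The eligible participants will receive study OK lenses during the dispensing visit". No spare or replacement lens is mentioned for that visit.

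Section VII, Statistical Analysis, takes these data as a time "effect (baseline, 6month and 12 month) and between-group differences in lens deposition levels", among other measures, which "will be tested with repeated measures ANOVAs (post-hoc tests) or Friedman test" with Bonferroni correction where appropriate. If the overall test is significant, post-hoc tests are to help confirm progressive worsening from baseline to 12 months. No eye term is named.

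**The concern.** The hypothesis is that spoilage, including deposits, gets steadily worse over baseline, 6 and 12 months, and the spoilage levels at different times are meant to inform when a lens should be replaced. Whether deposits go on rising after 6 months bears directly on that aim. In the assay, that comparison is always a left lens against a right lens. If the two sides differ systematically, for example through handling or cleaning order, the difference appears as change over time, and neither a larger sample nor a later choice of model can remove it.

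The second matter is one of consistency. The right lens is replaced at 6 months because the original goes to the assay, which implies that an assayed lens is not worn again. Yet the same assay is scheduled on the right lens at baseline, and that lens is apparently worn on to 6 months.

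**Working it through.** The protocol states no figure on this point, so there is none to reproduce.

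**Inputs from the protocol.** Eye assayed: right, right, left at baseline, 6 and 12 months (section III, item 4). Participants: 16 recruited, 12 needed (section IV). Significance level 0.05 (section VII); sidedness is not stated, and two-sided is assumed here. **Assumed:** a right-left difference *e* from 0 to 0.8 SD of the paired 12-minus-6-month difference, because the protocol gives none.

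**Step 1: can eye and time be separated?** The columns are intercept, 6 months, 12 months and left eye:

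| Assay | Intercept | 6 months | 12 months | Left |
|---|---|---|---|---|
| Baseline, right | 1 | 0 | 0 | 0 |
| 6 months, right | 1 | 1 | 0 | 0 |
| 12 months, left | 1 | 0 | 1 | 1 |

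The last two columns are equal, so the rank is 3 of 4 (2 of 3 for 6 against 12 months alone). With an additive eye effect:

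- E[L12 − R6] = (true 12-month minus 6-month change) + (L − R)
- E[L12 − R0] = (true 12-month minus baseline change) + (L − R)
- E[R6 − R0] = (true 6-month minus baseline change), with no eye term

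If the baseline value comes from an unworn lens and the sides differ only through wear, the second line describes accumulation in left eyes alone. The 6-month step still describes right eyes, so the two steps together do not trace one course over time.

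**Step 2: what would a given difference do?** Take the paired t test of 12 against 6 months with no true time effect. The statistic is noncentral t with n − 1 degrees of freedom and noncentrality *e*√n. For n=16 and *e*=0.5 the noncentrality is 0.5 × 4 = 2.0. Probability of a significant result at two-sided 0.05, without Bonferroni adjustment:

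| *e* (SD) | n=16 | n=12 |
|---|---|---|
| 0 | 0.050 | 0.050 |
| 0.2 | 0.116 | 0.097 |
| 0.3 | 0.203 | 0.158 |
| 0.5 | 0.465 | 0.353 |
| 0.8 | 0.848 | 0.714 |

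A Bonferroni correction would lower these rates but leave the shift in the estimate unchanged.

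**Step 3: does counterbalancing cure it?** Half the participants go right then left and half left then right. The design matrix then has full rank: 4 of 4, with the baseline value taken from the eye assayed at 6 months, or 3 of 3 for 6 against 12 months alone. The mean paired difference is (change + *e*) in one order and (change − *e*) in the other, so the average of the two order means is the change. In 40,000 simulated studies of 8 per order, this estimate was unbiased to simulation error (−0.001 and 0.000 SD), with type I error 0.051 at *e*=0.5 and 0.050 at *e*=0.8. Its standard error is SD × √(1/8 + 1/8) / 2 = 0.25 SD, the same as SD/√16.

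**Step 4: the baseline lens.** There are two readings of item 4. If the assay takes a lens out of wear, a right lens assayed at baseline cannot be the original lens collected at 6 months, unless a spare was used that the protocol does not mention. If the assay leaves the lens wearable, the reason given for replacing it at 6 months falls away. As written, the two statements do not fit together.

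**The case against.** The strongest reply has four parts.

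*The assay is peripheral.* The primary outcome is the spoilage grading score, the secondary outcomes are comfort and ocular surface changes, and the sample size is built on grading differences. This stands, and it limits the weight of the point: the order of eyes in the assay does not bias the gradings directly.

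*No right-left difference has been shown.* Both lenses are of one material, are cared for with the same solutions and are worn by the same person. Grading both lenses at equal wear up to 6 months might reveal a systematic difference. It stands that the size is unknown and may be nil. But a check on a 0-to-4 grade is only indirect evidence about assayed protein and lipid, and the assay data themselves cannot show that the difference is absent.

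*Changing eyes is necessary.* The right lens is renewed at 6 months, so only the left has 12 months of wear. This justifies using the fellow eye at 12 months. It does not justify the same order for everyone. Values from different lenses are unavoidable once an assayed lens leaves wear, and that is not a fault in itself.

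*The baseline lens may be a duplicate.* A reader might infer that the baseline assay destroys the dispensed lens and that up to 16 would be lost. The documents do not support that. They never say that the assay is destructive, and calling the 6-month lens the original one suggests that it was not used up earlier. What stands is that the source of the baseline value is not given.

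**Conclusion.** The point holds for the protein and lipid assay and for its two comparisons that involve 12 months. Under the fixed order no analysis plan can separate eye from time in these comparisons, so this is a feature of the design and not a detail left for later. A reader might go further and call all three time points confounded, but baseline and 6 months are both right-eye lenses. A reader might also call the result biased. That requires a real right-left difference, which the protocol neither states nor excludes; the illustrative rates at n=16, from 0.05 with no difference to 0.47 at 0.5 SD, rest on assumed values and an unadjusted two-sided test. Nor does the point undermine the primary outcome.

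It still merits action. The assay is the study's laboratory measure of deposition, it enters the test of progressive worsening, and the remedy needs no more lenses. The baseline matter is an internal inconsistency to be reconciled, not proof that a baseline value is unobtainable.

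**What to change.** 1. Before the first 6-month visit, draw up a random list allocating each of the 16 participants to have the right or the left lens taken and replaced at 6 months, 8 to each. Assay the fellow, unreplaced lens at 12 months.
2. Analyse the paired 12-minus-6-month difference with a term for eye order, that is, average the two order means. This stays free of an additive eye effect if dropout leaves the orders unequal in number.
3. State in section III, item 4, and in Table 3 which lens supplies the baseline value, for example an unworn duplicate or blank of the same material, and reconcile this with the reason given for the 6-month replacement. Baseline need not be dropped from the analysis if that source is valid.

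The cost is a short allocation list, a minor amendment and one degree of freedom (14 in place of 15 at n=16). One replacement lens per participant at 6 months is needed either way. For participants whose right lens has already been taken at 6 months, the order can no longer be changed. If that applies to all of them, the 12-month assay contrasts should be reported as not separable from a right-left difference.

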The investigators are mindful of the need to actively reflect upon the balance between benefits and risks of a project while it is being conducted and the degree to which continuation of the study is justified should an adverse event be reported. Thus, any adverse event will be reported and handled in accordance with HREC Adverse Event Reporting Guidelines.

5. Benefits of the research outweigh the risk of harm or discomfort:

Eye infections associated with orthokeratology (OK) lenses is generally considered a low-incidence risk, particularly with proper lens care and adherence to recommended replacement schedules. While investigators cannot guarantee the direct benefits from this research, the potential benefits may include clear vision without needing to wear glasses or contact lenses during the day. The benefit of participating in this research study will contribute to the development of strategies that are aimed to minimise severe form of eye disease associated with long-term use of spoiled OK lenses.

Early Termination

The techniques proposed have been applied by the same and different investigators previously in multiple clinical studies and have not ever resulted in termination of any of these studies due to adverse events, so this is very unlikely. However, consideration for early termination of the study would occur if a serious adverse event is reported or if all collected data were of insufficient quality for analysis after repeated attempts at improving recording techniques and methods.

VII. STATISTICAL CONSIDERATIONS.

Sample size calculations

We are planning a study with an ordinal data response variable from matched pairs of study participants. We estimate that the difference in the lens spoilage grading between matched pairs is normally distributed with a standard deviation 0.9. To detect a true mean difference of 1.90 between pairs, we will need 12 subjects to achieve 80% power, assuming a Type I error rate of 0.05. To account for a 20% dropout rate, a total of 16 participants will be recruited. We will keep screening until we have met that target. However, since this sample size was not determined using the exact methodology relevant to the current study, we will collect pilot data as part of the research. Based on the pilot data results, we will recalculate the final sample size to ensure the statistical power is appropriately adjusted for the use of orthokeratology (OK) lenses.

Statistical Analysis

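### The sample-size statement contradicts itself: SD 0.9, difference 1.90 and alpha 0.05 need 4 or 5 pairs for 80% power, and 12 pairs give more than 99.99%

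*Protocol*

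**What the plan says.** The same calculation stands in three places of the Protocol: the Summary (Planned sample size), Section IV (Number of participants) and Section VII (Sample size calculations). It describes an ordinal response from matched pairs and assumes that "the difference in the lens spoilage grading between matched pairs is normally distributed with a standard deviation 0.9". It then concludes: "To detect a true mean difference of 1.90 between pairs, we will need 12 subjects to achieve 80% power". Alpha is set at 0.05. The allowance for loss follows: "To account for a 20% dropout rate, a total of 16 participants will be recruited". The protocol does not say whether the test is one- or two-sided, which two visits form the pair, or which of the 0 to 4 grades defined in Section III (deposits, scratch extent, scratch magnitude) the 1.90 refers to.

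Section VII alone adds a caveat. The size did not come from a method matched to this study, pilot data will be collected, and the final number will be recalculated from them.

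The Statistical Analysis part of Section VII compares baseline, 6 months and 12 months by repeated measures ANOVA "or Friedman test, with Bonferroni correction, where appropriate", with post-hoc tests if the overall result is significant.

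**The concern.** A mean difference of 1.90 against an SD of 0.9 is a standardised effect of about 2.1. For a paired test that is very large and should need only a handful of pairs. A requirement of 12 at 80% power points to a much smaller effect or a much larger SD, so the number of subjects, the power or one of the two inputs must be wrong.

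This calculation is the only justification given for the number enrolled. If 1.90 and 0.9 are both right, the stated power is wrong and the study is far larger than that target needs. If the SD is really above 2, the study is much less sensitive than an SD of 0.9 implies. If the difference is really nearer 0.8, the protocol misreports its own target. The planned recalculation also needs a target difference and an SD that agree with each other, and the text does not supply them.

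**Working it through.** **Inputs**, all from Section VII (Sample size calculations) and repeated in the Summary and Section IV:
- SD of paired differences: 0.9
- true mean difference: 1.90
- type I error rate: 0.05, sidedness not stated, so both are tried
- power: 80%
- stated result: 12 subjects, then 16 after 20% dropout

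**Formula.** For a paired t-test with n pairs, the test statistic follows a noncentral t distribution with n − 1 degrees of freedom and noncentrality (difference/SD) × √n. Power is the probability that it exceeds the critical t value (in absolute value for a two-sided test). The standardised effect is 1.90/0.9 = 2.11.

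**Attempt to reproduce 12.**

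| Pairs | Noncentrality | Power, two-sided 0.05 | Power, one-sided 0.05 |
|---|---|---|---|
| 3 | 3.66 | 50.5% | 74.7% |
| 4 | 4.22 | 79.4% | 93.1% |
| 5 | 4.72 | 93.4% | 98.4% |
| 6 | 5.17 | 98.2% | 99.7% |
| 12 | 7.31 | above 99.99% | above 99.99% |

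The requirement is 5 pairs two-sided or 4 one-sided. The figure of 12 is not reproduced.

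**Other readings of the same inputs at 80% power:**
- normal approximation, (0.9 × (1.96 + 0.84)/1.90)² = 1.76: 2 pairs
- Wilcoxon signed-rank, two-sided (simulated): 6 pairs, power about 91%
- sign test, two-sided: 6 pairs, power 90%
- two-sided alpha 0.0167: 6 pairs
- 0.9 taken as the SD at each visit with no correlation, so SD of differences 0.9 × √2: 6 pairs
- inputs swapped (difference 0.9, SD 1.90): 37 pairs
- two independent groups: 5 per group, 10 in total, but this contradicts the matched-pairs design

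Even two-sided alpha 0.01 with 95% power needs only 8 pairs. None of these gives 12.

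**What 12 pairs at 80% power implies.** Solving the two-sided formula for the effect at n = 12 gives difference/SD = 0.889. That fixes a ratio, not a pair of values:
- with SD 0.9, the difference is 0.889 × 0.9 = 0.80 (power for 0.80 is 75.7% at 11 pairs and 80.0% at 12)
- with difference 1.90, the SD is 1.90/0.889 = 2.14

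If the test is one-sided, the difference at SD 0.9 is 0.69.

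**Sensitivity if SD 0.9 is right** (80% power, two-sided):

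| Completers | Alpha 0.05 | Alpha 0.05/3 = 0.0167 |
|---|---|---|
| 12 | 0.80 grade | 0.97 grade |
| 16 | 0.67 grade | 0.81 grade |

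The last column applies only if the Bonferroni correction covers the three pairwise visit comparisons.

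**Dropout.** 12/(1 − 0.2) = 15, against 16 stated. The extra participant is harmless and is not part of this point.

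**The case against.** Three objections carry weight. First, Section VII declares the size provisional and plans to recalculate it. That lowers the consequence. However, the caveat concerns how well the calculation applies to this study and does not explain how 12 follows from its inputs. It is also absent from the Summary and Section IV.

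Second, on the stated inputs the error is on the safe side: 12 pairs are more than enough for 1.90, and this is a single-group observational study. That stands if both inputs are right. It fails if the SD is really near 2.14, and the text cannot exclude that.

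Third, 0.80 is back-solved under a two-sided test. This is correct, so 0.80 should not be taken for the sponsor's intended target. It is only the sensitivity that follows if SD 0.9 is kept.

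A reader might also infer three stronger things that the documents do not support:
- **That the study can detect only a shift of nearly half the 0 to 4 scale.** A target difference is not a detection floor, and the protocol does not say whether 1.90 refers to one grade or a combination.
- **That the 80% power matches no planned analysis.** Baseline against 12 months is a paired contrast among the planned post-hoc tests.
- **That the calculation is wrong for ignoring a split alpha.** The Bonferroni wording is conditional, the figure 0.0167 is not in the protocol, and powering one key contrast at 0.05 is a common simplification.

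**Conclusion.** The statement is wrong as written. On its own inputs, 80% power needs 5 pairs two-sided or 4 one-sided, against 12 stated, and power at 12 is above 99.99%, against 80% stated. This rests on a paired t-test with normally distributed differences, which is the protocol's own assumption; rank and sign tests need 6 and leave the conclusion unchanged. Which figure is wrong cannot be settled from the documents, and the planned recalculation does not settle it. The fault lies in the justification. It does not show that the study is underpowered, nor that 16 is the wrong number to enrol.

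**What to change.** Trace the source of the calculation and correct the sentence in the Summary, Section IV and Section VII. State sidedness, the contrast (for example baseline against 12 months) and the grade to which the difference refers. Then:
- If SD 0.9 and difference 1.90 are both intended, replace 80% with the true power at 12 pairs, above 99%.
- If SD 0.9 is right and the difference is not, state that 12 evaluable participants give 80% power for a mean change of 0.80 grade at two-sided alpha 0.05, or 0.67 grade if all 16 complete.
- If 1.90 is right and the SD is not, state the SD and its source; 80% power at 12 pairs implies about 2.14.

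Optionally, add that if the Bonferroni correction covers three pairwise comparisons, the detectable change with 12 is about 0.97 grade at SD 0.9. Settle the target difference and SD before the pilot-based recalculation, and mention that recalculation in the Summary and Section IV as well.

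The cost is a wording change in three places. This error alone is no reason to alter the planned enrolment of 16, and no visit or procedure changes.
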